Study Title: Impact of Sleep Restriction on Cardiometabolic Risk Factors in Pre- and Postmenopausal Women

Short Title: Impact of Sleep Restriction in Women

ClinicalTrials.gov ID: NCT02835261

Document Date: 2016 February 16 (original); 2020 July 21 (final revision); 2025 October 09

(submitted)

SPECIFIC AIMS

The overall goal of this project is to test the hypothesis that long-term, sustained SR, in women, will lead to increased cardio-metabolic risk. This will be characterized by increases in visceral adiposity, unhealthy lifestyle behaviors (poor dietary quality and low physical activity) and cardio-metabolic risk factors (blood pressure, glucose intolerance) relative to HS. We expect these changes to be worse in pre- compared to post-menopausal women.

Specific Aim 1. To assess the effects of SR on cardio-metabolic risk profile, relative to HS.

Hypothesis 1: Prolonged SR will lead to increased blood pressure and reduced glucose tolerance relative to HS.

Specific Aim 2. To assess the effects of SR on adiposity, relative to HS, over a 6-week period. *Hypothesis 2:* Prolonged SR will lead to increased visceral adiposity, assessed by magnetic resonance imaging (MRI), relative to HS.

Specific Aim 3. To assess the effects of SR on diet and physical activity level.

Hypothesis 3a: Prolonged SR will lead to reduced physical activity relative to HS.

Hypothesis 3b: Diet quality will be reduced with SR relative to HS, as reflected by increased intake of snacks, fat, and simple sugars.

Exploratory Hypothesis: The effects of prolonged SR on adiposity and cardio-metabolic risk factors will be greater in pre-menopausal women relative to post-menopausal women.

RESEARCH DESIGN & METHODS

Study population & Sample size determination

We will enroll 80 participants and expect 50 to complete the study. This drop-out rate accounts for participant non-compliance and withdrawal from the study. In our previous *Sleep Study*, our completion rate was 90% (27/30). We expect a larger drop-out rate in the proposed study due to the longer duration of each treatment phase, and also, some participants may be dismissed from the study from their inability to achieve and maintain the 1.5 h average weekly SR.

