This study will be a randomized, crossover, outpatient SR study with 2 phases of 6 weeks each. Sleep duration in each phase will be the participant's regular bed- and wake-times during the HS phase and HS minus 1.5 h in the SR phase. During the HS phase, participants will be asked to follow a fixed bedtime routine based on their screening sleep schedule. During the SR phase, participants will be asked to keep their habitual wake time constant but delay their bedtime to achieve a reduction of 1.5 h in total sleep time. A delay in bedtimes was chosen rather than advancing wakeup time because it likely most closely reflects differences in sleep timing behavior between short and normal sleepers. Spaeth and colleagues have also shown that restricting sleep to the latter portion of the night is associated with increased food intake and weight gain relative to HS (8). We also considered providing fixed bed- and wakeup times for all women but decided to provide individualized bedtimes and wakeup times to reduce variability in our sample.

On the first day of each study phase (baseline), participants will come to the Clinical Research Resource (CRR) of the Irving Center for Clinical and Translational Research (CTSA) at CUMC in the morning after an overnight, 12 h fast. Participants will have anthropometric measurements taken and will then be taken to the department of Radiology to undergo magnetic resonance imaging (MRI) scanning to assess body composition. They will then return to the CRR for an oral glucose tolerance test. Participants will begin the fixed bedtime routine that night. These baseline measurements will be

repeated at endpoint, 6 weeks later. Body weight and waist circumference will be measured weekly and fasting blood samples will be taken bi-weekly during adherence check visits v.

Recruitment and blinding

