Linear Mixed Model Analyses. We will fit a linear mixed model to analyze the data. Treatments (sleep: SR vs. HS) will be used as fixed effects and subject will be used a random effect. The other independent variables (covariates) will be age, baseline BMI, and race/ethnicity. If required anywhere in the analysis plan, p-values will be adjusted for multiple comparisons.

Specific Aim 1. To assess the effects of SR on cardio-metabolic risk profile, relative to HS. (Hypothesis 1: Prolonged SR will lead to increased blood pressure and reduce glucose tolerance relative to HS.) We will perform a repeated measure linear mixed model analyses separately with each of blood pressure and glucose tolerance measures (each in a separate model) as the response and sleep (SR vs. HS), time, sleep-time interaction and the covariates as independent variables, with data from all time points combined. Subject will be used as a random effect. Additionally, we will also use the change from baseline to week-6 in each of blood pressure and glucose tolerance measures as response variables in separate regressions, where sleep (SR vs. HS) and the covariates will be used as the independent variables. Paired one-sided t-test and Wilcoxon test will be used to determine whether the SR is associated with increased blood pressure and reduced glucose tolerance vs. HS.

Specific Aim 2. To assess the effects of SR on adiposity, relative to HS, over a 6-week period. (Hypothesis 2: Prolonged SR will lead to increased visceral adiposity, assessed by MRI, relative to HS.) We will perform a repeated measure linear mixed model analyses separately with each visceral adiposity variable (as observed by MRI) (each in a separate model) as the response and sleep (SR vs. HS), time, sleep-time interaction and the covariates as independent variables, with data from all time points combined. Subject will be used as a random effect. Additionally, we will also use the change from baseline to week 6 in each adipose tissue variable as response variables in separate regressions, where sleep (SR vs. HS) and the covariates will be used as the independent variables. Paired one-sided t-test and Wilcoxon test will be used to determine whether the SR is associated with increased adiposity variable relative to HS.

_

xiii See Amendment 2a

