Exploratory Hypothesis: The effects of prolonged SR on adiposity and cardio-metabolic risk factors will be greater in pre-menopausal women relative to post-menopausal women. We will first compute the effect of SR on adiposity and cardio-metabolic risk factors. This will be computed as the increase in SR from the baseline value of the SR-phase on each measure of adiposity and cardio-metabolic risk factors for each woman. Then these differences will be compared between pre- and post-menopausal women by means of a linear model analysis, one-sided unpaired t-test and Wilcoxon test. The comparison by linear models will be done by using the (SR vs. baseline) difference as the outcome (separately for each of adiposity and cardio-metabolic risk factors) and menopausal-status (pre- vs. post) and the covariates as independent variables. Paired one-sided t-test and Wilcoxon test will be used to determine whether the menopausal-status (greater in pre- vs. post-, to be used as the two groups for the tests) is associated with greater average difference (SR vs. baseline) in adiposity and cardio-metabolic risk factors.

ETHICAL ASPECTS OF THE PROPOSED RESEARCH Protection of human subjects

All personnel involved in this project, including fellows who will be trained as part of the Center grant, will undergo human subjects research training. Courses include ethical considerations of human subjects research and health information privacy rules. Research will not be performed until approval from our Institutional Review Board is obtained. All participants will be informed of the study procedures during the screening and consenting process and will be given the opportunity to ask questions about the study. Furthermore, participants will be informed that they can withdraw from the study at any time without jeopardizing their future care at our medical center.

All data will be kept on file coded (de-identified) with a study number and without any specific identifying personal health information. Study data will be stored on password-protected, encrypted end-point devices. All paper files will be stored in locked cabinets. Imaging data will be stored (de-identified) in a secure computer database that is protected by firewalls and passwords. MRI data will be transferred to the New York Image Reading Center via secure servers. Only personnel immediately involved in the study will have access to study files and documents.

Potential risks & risk management

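### The exploratory pre- versus post-menopausal comparison uses only the change within the sleep-restriction phase and leaves out each woman's habitual-sleep phase

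*Combined protocol and SAP*

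**What the plan says.** - **Effect definition.** Statistical analysis plan, Exploratory Hypothesis: "This will be computed as the increase in SR from the baseline value of the SR-phase". This SR-minus-baseline difference is the outcome. Menopausal status and the covariates (age, baseline BMI, race/ethnicity) are the predictors.
- **Tests.** The same paragraph first names a "linear model analysis, one-sided unpaired t-test and Wilcoxon test". It then says "Paired one-sided t-test and Wilcoxon test will be used to determine whether the menopausal-status" is associated with a greater average difference, with pre- and post-menopausal women as the two groups.
- **Goal.** Specific Aims, opening paragraph, expects increases in adiposity and in "cardio-metabolic risk factors (blood pressure, glucose intolerance) relative to HS. We expect these changes to be worse in pre- compared to post-menopausal women".
- **Hypothesis sentence.** It does not mention HS: "The effects of prolonged SR on adiposity and cardio-metabolic risk factors will be greater in pre-menopausal women relative to post-menopausal women".
- **Design.** Overview of study design: "This study will be a randomized, crossover, outpatient SR study with 2 phases of 6 weeks each". MRI and the glucose tolerance test are done at the start of each phase and repeated six weeks later. Seated blood pressure is taken weekly.
- **Power.** Study population & Sample size determination gives mean paired differences of 0.69 ± 0.36 (fat mass) and 0.91 ± 0.65 (weight gain), hence effect sizes of 1.92 and 1.4. It concludes that power exceeds 80% for paired tests and also suffices for pre/post differences. It states no group split, target gap or alpha.
- **Ambulatory blood pressure.** Planned at baseline, 3 and 6 weeks of each phase. Amendment 2e leaves one endpoint measure.

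**The concern.** A change from baseline within one phase is an uncontrolled before-after measure. It contains the SR effect together with whatever would have happened over six weeks anyway: season, effects of taking part, regression to the mean, natural weight change. Drift common to both menopausal groups cancels when the groups are compared. Drift that differs between them does not, and the planned contrast cannot tell it from a difference in the SR effect. The HS phase exists to remove it, and Aims 1-3 use it for that purpose. A positive result would be read as a larger SR effect in pre-menopausal women, and a real difference could also be hidden.

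Two smaller matters sit in the same analysis. A paired test needs pairs, and pre- and post-menopausal women are different people. A paired effect size describes the average SR effect, so it says nothing about power to detect a gap between two groups.

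**Working it through.** **1. What the two contrasts estimate.** Let b be the background six-week change and τ the SR-versus-HS effect in a group. The mean SR-phase change is b + τ and the mean HS-phase change is b.

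- SR-only contrast: (τ_pre − τ_post) + (b_pre − b_post)
- Double difference, (SR week 6 − SR baseline) − (HS week 6 − HS baseline): τ_pre − τ_post

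The bias of the first is b_pre − b_post, one for one.

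**2. Size of the effect, for illustration.** Assumptions, none in the documents: 25/25 split of the 50 expected completers, one-sided 5%, τ_pre = τ_post. The noncentrality of the two-sample t-test is δ/√(1/25 + 1/25) = 3.536 δ, with 48 df and δ in SDs of the change.

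| Background difference δ (SD) | SR-only test rejects |
|---|---|
| 0 | 5% |
| 0.1 | 9.7% |
| 0.25 | 22% |
| 0.5 | 54% |

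In 20,000 simulated trials at δ = 0.5, the SR-only test rejected in 54.0% and the double difference in 5.0%. With a true gap of 0.5 SD, a background difference of −0.5 SD and a correlation of 0.5 between a woman's two changes, the figures were 4.9% and 54%.

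**3. The plan's power figure.** 0.69/0.36 = 1.917 and 0.91/0.65 = 1.40, as stated. With 50 pairs the paired t-test has more than 99.9% power at both, so the claim of over 80% is met for SR versus HS.

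**4. Power for a pre/post gap.** Assumptions: 50 completers, 25/25, no covariates, the sample-size section's SDs refer to SR versus HS and hold in each group. For 80% power, one-sided 5%, the gap must be 0.713 SD (0.809 two-sided). For the double difference:

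- Fat mass: 0.713 × 0.36 = 0.257; 0.257/0.69 = 37% of the mean effect
- Weight: 0.713 × 0.65 = 0.464; 0.464/0.91 = 51%
- At 35/15 the gap is 0.778 SD: 0.280/0.69 = 41% and 0.506/0.91 = 56%

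The planned SR-only change has a different SD. With equal phase variances and correlation r between a woman's two changes, SD(double difference) = √(2(1 − r)) × SD(SR change). The listed SDs must therefore be divided by that factor:

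| r | √(2(1 − r)) | Gap, fat mass | Gap, weight |
|---|---|---|---|
| 0 | 1.41 | 26% | 36% |
| 0.5 | 1.00 | 37% | 51% |
| 0.75 | 0.71 | 53% | 72% |

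Example at r = 0: 0.713 × 0.36/1.414 = 0.182; 0.182/0.69 = 26%.

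**5. Price of the double difference.** Where the SR-only test has 80% power (25/25, one-sided 5%), the double difference has about 54%, 65%, 80% and 97% at r = 0, 0.25, 0.5 and 0.75. The documents give no r.

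**6. Age as a covariate.** Age is closely tied to menopausal status. With assumed uniform ages of 20-50 (pre) and 50-65 (post), the within-group variance is (75 + 18.75)/2 = 46.9 and the between-group part (22.5/2)² = 126.6. The variance inflation is (46.9 + 126.6)/46.9 = 3.7, and the detectable gap becomes 0.713 × √3.7 = 1.37 SD. With overlapping ages of 35-52 and 45-65 the inflation is about 2.2 and the gap about 1.05 SD.

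**The case against.** The hypothesis is labelled exploratory, and its own sentence speaks only of the effects of prolonged SR. A reader might infer that the computation contradicts the hypothesis. It does not: the mismatch is with the overall goal and with the design. That part of the objection stands.

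The bias may be nil, and common drift cancels. The remedy trades an unquantified bias for a possible loss of precision. This also stands, and it is a reason to keep the SR-only change beside the new contrast. It does not justify leaving the uncontrolled measure as the only one, because the planned analysis cannot show whether the bias is present.

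The paired sentence is editorial. The same paragraph already names the unpaired test, and the later wording looks carried over from Aims 1-3. A reader might infer that an invalid test is the only one planned; the text does not support that.

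The double difference has weak spots of its own. A difference between phases in six-week change enters it with opposite sign in the two sequences, and the documents describe no stratification of randomization by menopausal status. Adjusting for age can widen the interval greatly, though the planned linear model already carries that cost. Both belong in the fix.

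Ambulatory pressure is a side issue. A reader might infer that Amendment 2e disables the blood-pressure part of Aim 1. It does not, since seated pressure remains weekly; only a "change from baseline to week-6 in each of blood pressure and glucose tolerance measures" based on ambulatory readings is lost.

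**Conclusion.** The point holds, at minor to moderate weight. The exploratory contrast omits the comparator that the stated goal names and the crossover supplies, so it cannot separate a menopausal difference in the SR effect from one in background change. That conclusion follows from the definition and needs no assumed figure. The 22% and 54% rejection rates are illustrations under the assumed split, alpha and background differences; they are not estimates of this trial's error rate.

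The paired sentence is a wording error. The pre/post power statement is unsupported by the effect sizes given. A reader might infer that the comparison is underpowered, but the documents set no target gap, so only the detectable gap can be stated. The 37% and 51% describe the SR-minus-HS contrast, and they fit the planned SR-only change only if r = 0.5. The SR-versus-HS comparisons of Aims 1-3 are not affected by the main point.

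**What to change.** - Make the main exploratory contrast an unpaired comparison by menopausal status of (SR week 6 − SR baseline) − (HS week 6 − HS baseline), by linear model, two-sample t-test and rank-sum test. Include treatment sequence in the linear model. Keep the SR-only change as supportive.
- Report the linear-model contrast with and without age.
- Delete the sentence naming paired tests for the two menopausal groups.
- State that the paired effect sizes do not support the pre/post power claim, and give the detectable gap with its assumptions.
- For ambulatory blood pressure, if the endpoint measure was taken in both phases, compare the SR and HS endpoints (Aim 1) and compare their difference between menopausal groups.
- The Amendments section describes accrual and procedures in the past tense. If data have been examined, label the change post hoc.

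Cost: no new data for MRI, glucose tolerance or seated blood pressure. Precision falls if r is below 0.5. Women without both phases drop out of the double difference; the plan expects 30 of 80 not to complete, and any of them with a full SR phase could have entered the SR-only analysis.
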